**End of Treatment Visit**

The following procedures will be performed for all patients 28 days ( $\pm 7$  days) after the last dose of oral CO-1686:

- Physical examination
  - Including a vision check as part of a standard physical exam
- Weight
- Vital signs (blood pressure, pulse, and temperature)
- Concomitant medications and procedures since last visit

- 12-lead ECG (in triplicate, 10-sec tracings > 2 min apart)
- Fasting serum chemistry (includes fasting glucose)
- Hematology
- Serum pregnancy test for women of childbearing potential
- AE monitoring (until 28 days after last dose of oral CO-1686; then only ongoing serious adverse events (SAEs) are followed until resolution or stabilization)
- Collection and review of patient diary
- Contraceptive counseling

## LIST OF ABBREVIATIONS

AE	Adverse event
BSA	Body surface area
CR	Complete response
CRF	Case report form
DCR	Disease control rate
DLT	Dose-limiting toxicity
HRQOL	Health-related quality of life
ICH	International Conference on Harmonization
IRR	Independent radiology review
LDH	Lactate dehydrogenase
MedDRA	Medical Dictionary for Drug Regulatory Activities
NSCLC	Non-small cell lung cancer
ORR	Objective response rate
OS	Overall survival
PD	Progressive Disease
PFS	Progression-free survival
PR	Partial response
QOL	Quality of life
RECIST	Response Evaluation Criteria In Solid Tumors
SAE	Serious adverse event
SAP	Statistical analysis plan
SD	Stable disease
SLD	Sum of longest diameters
StDev	Standard deviation
TEAEs	Treatment-emergent adverse events
ULN	Upper limit of normal
WHO	World Health Organization

## 1 INTRODUCTION

This document describes the statistical analyses and data presentations to be performed for Clovis Oncology protocol CO-1686-008 “A Phase 1/2, Open-Label, Safety, Pharmacokinetic and Preliminary Efficacy Study of Oral CO-1686 in Patients with Previously Treated Mutant EGFR Non-Small Cell Lung Cancer (NSCLC)”. This statistical analysis plan (SAP) provides a comprehensive and detailed description of the strategy, rationale, and statistical techniques to be used to assess the efficacy and safety of CO-1686 in previously treated mutant EGFR NSCLC patients.

This version of the Statistical Analysis Plan (SAP) provides details of the statistical analyses that will be presented in the NDA and MAA. The majority of the analyses in this SAP are from the original protocol and subsequent amendments.

All statistical analyses detailed in this SAP will be conducted using SAS® Version 9.1 or higher.

## 2 OVERALL STUDY DESIGN AND OBJECTIVES

### 2.1 Study Objectives for Phase 1

#### 2.1.1 Primary Objectives

- To evaluate the toxicity profile of escalating doses of CO-1686 and to determine the maximum tolerated dose (MTD) and recommended Phase 2 dose (RP2D)
- To characterize the PK profile of CO-1686

#### 2.1.2 Secondary Objectives

The secondary objectives of this study are:

- To characterize the PK profile of CO-1686 after a high-fat breakfast vs in the fasted state
- To evaluate the effects of CO-1686 on the QT/QTc interval
- To evaluate tumor response (overall response rate [ORR] + duration of response) of CO-1686

#### 2.1.3 Exploratory Objectives

- To characterize lung-cancer and treatment-related symptoms in patients at baseline and in response to CO-1686 using the Dermatology Life Quality Index, the EORTC OLCQ-LC13, and the EORTC QLQ-C30
- To explore the concordance of T790M detected in tumor versus that detected in blood
- To determine if T790M is detectable in urine

### 2.2 Study Objectives for Phase 2

#### 2.2.1 Primary Objectives

- To evaluate tumor response (ORR + duration of response) to CO-1686 in patients with a T790M mutation

### 2.2.2 Secondary Objective(s)

The secondary objectives of this study are:

- To evaluate objective response rate (ORR), duration of response, and progression-free survival (PFS) in patients treated with CO-1686
- To evaluate the toxicity and tolerability of CO-1686
- To evaluate overall survival (OS), disease control rate (DCR) and progression-free survival in patients treated with CO-1686
- To determine pharmacokinetics (PK) of CO-1686 using population PK (POPPK) methods and explore correlations between PK, exposure, response, and/or safety findings
- To characterize lung-cancer and treatment-related symptoms in patients at baseline and in response to CO-1686 using the Dermatology Life Quality Index, the EORTC QLQ-LC13, and the EORTC QLQ-C30
- To evaluate the effects of CO-1686 on the QT/QTc interval

### 2.2.3 Exploratory Objective(s)

The exploratory objectives of phase 2 of this study are:

- To evaluate clinical benefit of continued CO-1686 treatment following disease progression
- To explore the concordance of T790M detected in tumor versus that detected in blood

## 2.3 Trial Design and Study Procedures

This study will include 2 parts:

- Phase 1: Dose-escalation Period with 21-day cycles; optional Treatment Extension Period starting on Day 22
- Phase 2: Evaluation of activity and safety in patients with the T790M EGFR mutation who have:
  - Cohort A
    - Progressed on EGFR directed therapy (irrespective of the number and order of previous lines of NSCLC therapy) (Dose levels of 750 mg BID, 625 mg BID and 500 mg BID)
    - or
    - Cohort B
      - Progression on the first single agent EGFR directed therapy received and also had no more than one previous line of chemotherapy (Dose levels of 750 mg BID, 625 mg BID and 500 mg BID)
      - or
      - Cohort C

- Signed consent for the study, and fulfils eligibility, but with discordance between local (T790M positive) and central (T790M negative) T790M results, or had no central test result due to inadequacy of the tissue specimen and known to be T790M positive by local test (Dose level of 625 mg BID).

### **2.3.1 Schedule of Assessments**

The procedures and assessments to be performed during the study are outlined in the Schedule of Evaluations in the protocol.

Patients in the Phase 2 portion of this study will receive CO-1686 at 500 mg BID, 625 mg BID or 750 mg BID. Treatment will continue until disease progression, patient withdraws consent for further treatment, or by investigator decision. Treatment can continue post-progression if, in the opinion of the investigator and approved by the sponsor, the patient has indolent progression with evidence of continued clinical benefit from treatment. The study consists of screening, treatment, and follow-up periods.

Within 28 days prior to Cycle 1 Day 1, patients will be screened and evaluated for eligibility for the study. During the treatment period, patients will return to the clinic for study drug and to be evaluated for safety and dosing compliance. Each cycle consists of 21 days. Imaging will be done at the end of Cycles 2, 4, and 6 (between Days 14 and 21) and every 3 cycles after Cycle 6 (between Days 14 and 21).

During the follow-up period, patients will be followed for survival, related serious adverse events (SAEs) and next therapy for NSCLC every 2 months until lost to follow-up, withdrawal of informed consent or sponsor decision. The follow-up data may be collected by visit, telephone or chart review.

## **2.4 Sample Size**

Total number of patients – up to approximately 715 (Phase 1 N≈110; Phase 2 N≈605)

- Phase 1: CO-1686 free base (completed) - 57 patients  
CO-1686 HBr - approximately 53 patients
- Phase 2:
  - Cohort A: approximately 40 patients for dose level 750 mg BID, up to approximately 275 patients for combined dose levels of 500 mg BID and 625 mg BID
  - Cohort B: approximately 40 patients for dose level 750 mg BID, up to approximately 150 patients for combined dose levels of 500 mg BID and 625 mg BID
  - Cohort C: up to approximately 100 patients at 625 mg BID

For the initial MAA and NDA submissions all patients enrolled in this trial at a dose of 500mg BID or 625mg BID by the 31st of December 2014 with a data cutoff date of April 29, 2015 will be used for both efficacy and safety conclusions. All other patients treated in CO-1686-008 enrolled by the 31st of December 2014 have a data cutoff date of December 31, 2014. The efficacy and safety profile for CO-1686 will be established by the combined patients treated in this study and Phase 1 study, CO-1686-008.

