**Table 6: Estimated Human Starting Doses and Safety Factors Based on Body Surface Area**

Species	GLP Toxicology Study Reference Dose (mg/kg/day)	Converted to BSA a (mg/m  )	Applied Safety Factor	Estimated Human MRSD	
				mg/m 2b	mg/day c
Rat	STD 10 = 400 d	2400	10	240 e	420
Dog	HNSTD = 1000 d	20,000	6	3333	5832

BSA = body surface area; GLP = Good Laboratory Practice; HNSTD = highest non-severely toxic dose; MRSD = maximum recommended starting dose; STD10 = severely toxic dose in 10% of rodents

a Conversion for mg/kg to mg/m^2: rat (mg/kg) X 6; dog (mg/kg) X 20.

b MRSD = 1/10 STD10 (mg/m^2) in rodents or 1/6 HNSTD (mg/m^2) in non-rodents.

c Conversion factor from mg/m^2 to mg/day in humans using 1.75 m^2 for a standard adult body surface area.

d STD10 and HNSTD were determined in rat and dog 28-day GLP toxicology studies.

e One tenth of the rat STD10 is 240 mg/m^2/day.

### 3.5.3 Doses for Phase 2

A MTD was not reached in Phase 1 for any doses studied with the free-base or HBr CO-1686 formulations. The RP2D of 750 mg BID CO-1686 HBr was selected based on review of the pharmacokinetic, overall safety and preliminary efficacy data available in early 2014, and patients are actively enrolling in cohorts A (later-stage) and B (earlier-stage disease) at 750 mg BID under Amendment 4. Subsequently, as the Phase 1 data matured, the recommended dose was adjusted to 625 mg BID based on robust antitumor activity at lower doses (Figure 2) and anticipated optimal tolerability.

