### 6.2 Inclusion Criteria

All patients enrolling into **either Phase 1 or Phase 2** must meet all of the following inclusion criteria:

1. Histologically or cytologically confirmed metastatic or unresectable locally advanced NSCLC
2. Documented evidence of a tumor with one or more EGFR mutations excluding exon 20 insertion
3. Have undergone a biopsy of either primary or metastatic tumor tissue within 60 days of dosing with study drug and have tissue available to send to the sponsor lab or are able to undergo a biopsy during screening
  - a. No change (except for washout or dose adjustment if required to manage adverse effects) in antitumor therapy regimen is allowed between the biopsy and CO-1686 initiation.
4. Life expectancy of at least 3 months
5. Eastern Cooperative Oncology Group (ECOG) performance status of 0 to 1
6. Age  $\geq 18$  years
7. Adequate hematological and biological function, confirmed by the following screening laboratory values:
  - Bone Marrow Function
    - o Absolute neutrophil count (ANC)  $\geq 1.5 \times 10^9/L$
    - o Platelets  $> 100.0 \times 10^9/L$
    - o Hemoglobin  $\geq 9$  g/dL (or 5.6 mmol/L)
  - Hepatic Function

- Aspartate aminotransferase (AST) and alanine aminotransferase (ALT)  $\leq 3 \times$  upper limit of normal (ULN); if liver metastases,  $\leq 5 \times$  ULN
- Bilirubin  $\leq 2 \times$  ULN\*
- Renal Function
  - Serum creatinine  $\leq 1.5 \times$  ULN
- Electrolytes
  - Potassium and magnesium within normal range. Patients may receive supplements to meet this requirement

8. Written consent on an Institutional Review Board/Independent Ethics Committee-approved Informed Consent Form (ICF) prior to any study-specific evaluation

\* In Phase 1 and Phase 2, patients with documented Gilbert's syndrome and conjugated bilirubin within the normal range may be allowed into the study. In this event it will be documented that the patient was eligible based on conjugated bilirubin levels.

Patients enrolling into **Phase 1** must also meet the following inclusion criteria:

- Prior treatment with EGFR-directed therapy (e.g. erlotinib, gefitinib, neratinib, afatinib, or dacomitinib [PF299804]). Prior chemotherapy, including intervening chemotherapy, is allowed.
  - The washout period for an EGFR TKI is a minimum of 3 days
  - The washout period for chemotherapy is a minimum of 14 days
  - Any toxicity related to prior treatment must have resolved to Grade 1 or less

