Be willing and able to eat a high-fat breakfast on Day 1 of the study (*only applicable to food-effect cohort*).

Patients enrolling into **Phase 2 Cohort A** must also meet the following inclusion criteria:

- Disease progression confirmed by radiologic assessment while on treatment with EGFR-TKI (e.g. erlotinib, gefitinib, neratinib, afatinib, or dacomitinib). Prior chemotherapy, including intervening chemotherapy before planned initiation of CO-1686, is allowed.
  - The washout period for an EGFR TKI is a minimum of 3 days before planned Cycle 1 Day 1
  - The washout period for chemotherapy is a minimum of 14 days before planned Cycle 1 Day 1
  - Any toxicity related to prior treatment must have resolved to Grade 1 or less by Cycle 1 Day 1
- Documented evidence of T790M mutation in EGFR determined by PCR-based testing of the tumor tissue using the sponsor's central laboratory following disease progression on the most recent EGFR TKI therapy

- Measurable disease according to RECIST Version 1.1.
- Do not qualify for enrolment to Phase 2 Cohort B\*

\*Patients meeting eligibility criteria for Cohort B must be enrolled into this cohort rather than Cohort A.

Patients enrolling into **Phase 2 Cohort B** must also meet the following inclusion criteria:

- Disease progression confirmed by radiologic assessment while on treatment with the first single agent EGFR TKI (e.g., erlotinib, gefitinib, afatinib, or dacomitinib)
  - EGFR TKI treatment discontinued  $\leq$  30 days prior to planned initiation of CO-1686
  - The washout period for an EGFR TKI is a minimum of 3 days before planned Cycle 1 Day 1
  - No intervening treatment between cessation of single agent EGFR TKI and planned initiation of CO-1686
  - Previous treatment with  $\leq$  1 prior chemotherapy (excluding prior neo-adjuvant or adjuvant chemotherapy or chemoradiotherapy with curative intent)
  - Any toxicity related to prior EGFR inhibitor treatment must have resolved to Grade 1 or less by Cycle 1 Day 1
- Documented evidence of T790M mutation in EGFR as determined by PCR-based testing of tumor tissue using the sponsor's central lab following disease progression on the first single agent EGFR TKI.
- Measureable disease according to RECIST Version 1.1

Patients enrolling into **Phase 2 Cohort C** must also meet the following inclusion criteria:

- Must meet all inclusion criteria of either Phase 2 Cohorts A or B except for documented evidence of T790M mutation using the sponsor's central lab.

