##### **Objective Response Rate (ORR) - Primary Endpoint**

A primary endpoint in Phase 2 of the study (objective response rate) is the best response recorded from the start of the treatment until disease progression or recurrence. The frequency and percentages of patients with a best response of CR, PR, stable disease (SD), or progressive disease (PD) will be summarized for the tumor-evaluable and safety populations enrolled in Phase 2. The response rate (CR+PR) will also be presented with frequencies and percentages.

For patients who continue treatment post-progression, the first date of progression will be used for the analysis.

The ORR will be evaluated by the investigator with the primary analysis based on investigator assessment.

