### 3 GENERAL ANALYSIS CONVENTIONS

The summary tables will be presented for all patients treated with at least one dose of CO-1686 (safety population). Particular dose groups of interest, including patients from both Phase 1 and Phase 2, may be presented in the summary tables.

Quantitative variables will be summarized using descriptive statistics and may also be summarized categorically with frequencies and percentages. For variables registered on a continuous scale, the following will be presented: N, mean, standard deviation, median, minimum and maximum. Categorical variables will be presented using frequencies and percentages and the randomized treatment groups may be compared using Fisher's exact test. The Kaplan-Meier methodology will be used to summarize time-to-event variables. If estimable, the median together with a 95% confidence interval will be presented. The number of patients with events and the number of censored patients will also be presented.

All data will be used to their maximum possible extent but without any imputations for missing data.

Unless otherwise specified, baseline is defined as the last measurement on or prior to the first day of study drug administration.

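### SAP 2.4 and 11.1 let Phase 1 patients into the primary ORR and duration of response, although the protocol sets the primary ORR in Phase 2 patients, and SAP 15 does not list the change

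*SAP*

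**What the plan says.** Protocol 11.2.4.2 states that the best-response frequencies behind the primary ORR "will be summarized for the tumor-evaluable and safety populations enrolled in Phase 2". Duration of response, the other primary endpoint, is defined in the same Phase 2 section. That section opens by allowing efficacy results from the two phases to be shown together for selected dose groups. It does not make a pooled set the primary one.

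SAP 2.4 describes the data set for the initial NDA and MAA as "all patients enrolled in this trial at a dose of 500mg BID or 625mg BID" by 31 December 2014, with data to 29 April 2015, and says that these patients "will be used for both efficacy and safety conclusions". It adds that the efficacy and safety profile "will be established by the combined patients treated in this study and Phase 1 study, CO-1686-008". SAP 3 says: "Particular dose groups of interest, including patients from both Phase 1 and Phase 2, may be presented in the summary tables".

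SAP 11 limits efficacy evaluations to patients centrally confirmed as T790M positive, in the efficacy-evaluable and safety populations. SAP 11.1 defines the primary ORR by investigator assessment. Neither mentions phase. SAP 15 states the focus on 500 and 625 mg BID and lists six changes from the protocol; including Phase 1 patients in the primary analysis is not among them.

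On eligibility (protocol 6.2), Phase 1 asks for "Prior treatment with EGFR-directed therapy". Cohort A asks for "Disease progression confirmed by radiologic assessment while on treatment with" an EGFR TKI, and Cohort B makes the same demand for the first single-agent TKI. On the dose, protocol 3.5.3 says that "the recommended dose was adjusted to 625 mg BID based on robust antitumor activity at lower doses", and adds anticipated tolerability as a second reason.

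**The concern.** Read together, these sections change the population of the primary endpoint without saying so. This matters in three ways.

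- **Population.** The Phase 2 cohorts are defined by radiologic progression on a TKI. The central T790M filter in SAP 11 does not bring that requirement back for Phase 1 patients.
- **Reuse of data.** Protocol 3.5.3 and 5.1.2 cite Figure 2 for the activity that supported moving from 750 to 625 mg BID. Figure 2 shows centrally T790M-positive Phase 1 patients, who are the ones that pass the SAP 11 filter. Those treated at 500 or 625 mg BID would count again in the estimate offered for these doses.
- **Duration of response.** Phase 1 dosing with the HBr form ran from August 2013, and escalation was complete in January 2014. The 500 and 625 mg BID levels opened in Phase 2 only with Amendment 6. Phase 1 responders therefore have the longest possible follow-up at the April 2015 cutoff and could weigh on the Kaplan-Meier tail by more than their number. The documents do not allow this to be quantified.

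The closing sentence of SAP 2.4 also names CO-1686-008 as a Phase 1 study separate from this one, although SAP 1 identifies CO-1686-008 as this study. The intended pool cannot be read off with certainty.

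**Working it through.** **1. The plan's own count.** Phase 1: 57 + 53 = 110. Phase 2: 40 + 275 + 40 + 150 + 100 = 605. Total 715, as SAP 2.4 states.

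**2. Planned Phase 2 patients in the primary set.** Cohorts A and B at 500/625 mg BID: 275 + 150 = 425. Cohort C is left out, because its patients have a negative or missing central result and SAP 11 requires a positive one.

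**3. Phase 1 patients who could be pooled.**
- Lower figure: 8 centrally T790M-positive patients in protocol Table 5 (4 at 500 mg BID, 4 at 625 mg BID; cutoff 6 March 2014).
- Upper figure: 15 + 16 = 31 patients at these doses by 30 January 2014 (protocol 3.4.1), before any T790M filter.

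The T790M-positive number at the submission cutoff is not given.

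**4. Response rates.**
- Phase 1: Table 5 shows 2 + 2 = 4 partial responses at these doses. That is 4/8 = 50% of all, or 4/6 = 67% of those scanned (exact 95% interval about 22% to 96%). Over all doses in that table it is 14/22 = 63.6%. Range used: 50% to 63.6%.
- Phase 2: not given. Range assumed: 30% to 60%. The upper end matches the roughly 60% that the protocol synopsis reports for 40 T790M-positive patients in this study.

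**5. Share and shift.** Share w = n1/(n1 + n2). Shift in pooled ORR = w × (ORR1 − ORR2). The lowest shift uses 0.50 − 0.60 = −0.10 and the highest 0.636 − 0.30 = +0.336.

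| n1 (Phase 1) | n2 (Phase 2) | w | Lowest shift (points) | Highest shift (points) |
|---|---|---|---|---|
| 8 | 425 | 8/433 = 1.8% | −0.2 | +0.6 |
| 31 | 425 | 31/456 = 6.8% | −0.7 | +2.3 |
| 8 | 200 (assumed) | 8/208 = 3.8% | −0.4 | +1.3 |
| 31 | 200 (assumed) | 31/231 = 13.4% | −1.3 | +4.5 |

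The rows with 200 show what happens if Phase 2 was less than half enrolled by 31 December 2014; the documents do not give the number.

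By January 2014, 46 of about 53 planned HBr patients had been treated. If the other 7 had all gone to these doses, n1 would be 38 and w = 38/463 = 8.2%, again before the T790M filter. The shift would then run from −0.8 to +2.8 points.

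**6. Precision given up by leaving Phase 1 out.** At an ORR of 50%, the 95% half-width is 1.96 × √(0.25/n): 4.8 points at n = 425 and 4.6 points at n = 456.

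**The case against.** The other side has good points.

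- A reader might infer that every 500 and 625 mg BID patient enters the efficacy analysis. SAP 11 rules that out: central T790M positivity is required, which removes T790M-negative and unknown Phase 1 patients and, read strictly, Cohort C.
- A reader might infer that Phase 1 patients without measurable disease enter the response rate. SAP 4 requires measurable lesions for the tumor-evaluable population, and SAP 15 carries that set over into the efficacy population. Only the parallel analysis in the safety population lacks the requirement, and the protocol plans that analysis too.
- A reader might infer that 625 mg BID was picked simply as the best responder. Tolerability was a stated reason. In Table 5, 1000 mg BID had 3 of 3 responses and was not chosen. Protocol 5.1.2 says that no clear dose response could be shown.
- Protocol 5.1 describes patients in both parts as having failed an EGFR inhibitor, so many Phase 1 patients had probably progressed.
- SAP 2.4 is headed as sample size, and the analysis is descriptive: no null rate, alpha or success threshold is stated for the final ORR.

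These points limit the size of the problem and rule out a claim about its direction. They do not supply a phase restriction. SAP 2.4 states whose data support the efficacy conclusions, no later section narrows that by phase, and permission to show results together does not redefine a primary population. The Phase 1 criteria still did not require progression, and Phase 1 responses still contributed to the dose choice.

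**Conclusion.** The point holds as a change of primary population that SAP 15 does not list, with some reuse of data that informed the dose. It should be corrected, but it is unlikely to move the headline result much. At full planned enrolment the Phase 1 share is about 1.8% to 6.8% and the ORR shift about -0.7 to +2.3 points. This rests on the documented Phase 1 counts of early 2014, an assumed Phase 1 ORR of 50% to 64% and an assumed Phase 2 ORR of 30% to 60%. The share grows if fewer Phase 2 patients were enrolled by the cutoff.

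A reader might conclude that pooling inflates the ORR. The documents do not support this: 4 responses in 6 or 8 patients are compatible with a Phase 1 rate above or below that of Phase 2. The effect on duration of response is left unquantified.

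**What to change.** - In SAP 2.4 and 11.1, and in the duration-of-response analysis in SAP 11.2.1, define the primary set as centrally T790M-positive patients enrolled in Phase 2 at 500 or 625 mg BID.
- Report the pooled Phase 1 and Phase 2 result as supportive, with Phase 1 patients limited to those with documented progression on an EGFR TKI. No new filter for measurable disease is needed in the efficacy-evaluable set.
- Correct the sentence in SAP 2.4 that treats CO-1686-008 as a separate Phase 1 study.
- List any pooling of phases in SAP 15.

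The cost is a phase filter, some wording and a slightly smaller primary set. On the January 2014 count, at most 31 patients leave it, and the 95% half-width goes from about 4.6 to 4.8 points at an ORR of 50% under full enrolment.
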